7.0 VISIT SCHEDULE AND ASSESSMENTS

Table 7.1, lists all of the assessments and indicates with an “X”, the visits and when they are performed. For the phase Ib component only the first cycle will be utilized for determination of dose limiting toxicities. All data obtained from these assessments must be supported by the proper source documentation and placed in the patient’s chart.

7.1 TABLE OF ASSESSMENTS

Treatment Days	Screening Phase ¹		Treatment Phase: Chemoembolization	Treatment Phase: LEE011						Post Treatment Follow-up			Survival Phase
	Day -28 – Day -1	Day -7 – Day -1	7-14 days Following chemoembolization	Cycle 1		Cycle 2		C3	C4+	End of Treatment or Early Withdrawal (Within 15 Days of Last LEE011 Dose)	Safety Follow-Up (Within 30 Days of Last LEE011 Dose)	Efficacy Follow-Up	Survival Follow-Up Every 12 weeks
Visit Assessments				Day 1 ^{2,13}	Day 15	Day 1	Day 15	Day 1	Day 1				
Informed Consent	X												
Demographics	X												
Eligibility Checklist - Inclusion / Exclusion	X												
Med History	X												
Dx and Extent of Cancer (Staging)	X												
Physical Exam		X	X	X	X	X	X	X	X	X	X		
ECOG Status		X	X	X	X	X	X	X	X	X	X		
Height	X												
Weight		X		X	X	X	X	X	X	X	X		
Vital Signs		X	X	X	X	X	X	X	X	X	X		
CBC		X	X	X	X	X	X	X	X	X	X		

Chemistry (CMP)		X	X	X	X	X	X	X	X	X	X			
Cholesterol/Lipid Panel		X		X	X	X	X	X	X	X	X			
PT/INR		X	X	X	X	X	X	X	X	X	X			
Serum Pregnancy Test (WOCBP Only)		X							X	X				
Urinalysis		X								X	X			
Tumor Assessments with RECIST 1.1 ⁵	X			←----- Every 8 weeks ⁵ ----- -----→									X ⁵	
ECHO/MUGA	X													
ECG (12 – Lead)		X ³		X	X	X	X ³	X	X	X	X			
Adverse Events ⁶	X	X		X	X	X		X	X	X	X			
Conmeds ⁶	X	X		X	X	X		X	X	X	X			
Biomarker Tissue Collection (Biopsy) ⁷	X ⁷					X ⁷								
Biomarker Blood Collection ⁸		X		X		X		X	X	X				
LEE011 Study Drug (Oral) ⁹				X		X		X	X					
Patient Dosing Diary for LEE011 ⁹				X		X		X	X					
Chemoembolization (TACE) ¹⁰				X		X		X	X					
Discontinuation ¹¹											X			
Survival Follow-Up ¹²													X	

1. Screening assessments, apart from those listed above, must occur within 28 days of registration as per Table 7.1;
2. Vital Signs, ECOG Performance Status, Physical Exam, ECG, CBC, CMP, PT/INR, Lipid Panel, Serum Pregnancy Test (WOCBP Only), and Urinalysis should be performed within 7 days of the first treatment day (Cycle 1, Day 1). If there are any dose modifications or halting of drug in the phase II aspect, weekly hematology, comprehensive metabolic panels, and PT/INR laboratory investigations will be performed until the grade of adverse event leading to the modification or cessation is stable or a grade reduction occurs. In addition, following each chemoembolization the following will be done every other week for two cycles after each chemoembolization: physical examination, CMP, CBC, and PT/INR.
3. In order for an accurate evaluation of baseline QTc, a total of three (triplicate) 12-lead ECGs will be performed after resting in a supine position for 5-10 min, with a 2 minute interval between each ECG (triplicate ECG's at screening only). Subsequent ECG's will be performed after resting in a supine position for 5-10 min, on Day 1, C1D15, and C2D15 of each treatment cycle (single ECG's)prior to chemoembolization and LEE011;

4. For all treatment visits there is a general +/- 3 day window on assessments to take into account scheduling over public holidays, if not specifically specified otherwise;
5. Baseline scans can be completed within 28 days prior to registration. After baseline, radiological assessments (CT –chest/abdomen/pelvis or MRI – abdomen/pelvis) must be performed as outline in Table 7.1 (Every 8 weeks during the treatment phase). CT Chest must be performed at baseline. CT Chest during treatment will be performed if clinically indicated. A visit window of +/- 7 days is allowed. Once the patient has been discontinued from the study and enters the efficacy phase, radiological assessments (CT or MRI) will continue on the every 8 weeks schedule until progression or for the first 12 months, whichever comes first. After a year, radiological (CT or MRI) assessments will be performed every 12 weeks until progression.
6. AE/Conmeds will be assessed from consent until up to 30 days last dose of LEE001 or until resolution, whichever comes first. Conmeds will recorded up to 30 day prior to consent;
7. The biopsy performed during screening is for HCC diagnosis and RB positive status and must be performed for the subject to be eligible for the study. However, initial TACE can be performed following agreement of informed consent while RB proficiency is being determined. If patient is not RB proficient patient will be removed from the study as a screen failed and offered other treatment. If the patient has archival formalin fixed paraffin embedded tissue no additional baseline biopsy will be done. The post treatment biopsy is optional and for research purposes only (phase 2 only). If the subject consented to the research biopsy during the consent process, it will be performed during the 8th and 9th week of after initiating treatment of LEE011 and at least one chemoembolization. NOTE: LEE011 should be held for 24-48 hours prior to and after the second biopsy. These held doses will not be made up and noted on the patient's diary.
8. Biomarker blood collection is also an optional research procedure and the patient must have consented to the additional blood collection to participate (phase II only). Blood will be collected according to the schedule in table 7.1;
9. Patients will be treated with LEE011 (3 weeks on / 1 week off of a 28 day cycle) until disease progression, unacceptable toxicity, death, or discontinuation from the study treatment due to any other reason. The patient will complete a subject dosing log in order to ensure drug compliance. The patient will be provided a new dosing diary at each new treatment cycle and reviewed at the end of each cycle for compliance.
10. Patients will be treated with chemoembolization with up to 4 total chemoembolizations within the first 6 months from the initial chemoembolization.
11. Patients who discontinue treatment for reasons other than disease progression, death, start of new anti-neoplastic therapies, lost to follow-up, or withdrawal of consent to efficacy follow-up, then tumor assessments and patient reported outcomes must continue to be performed every 8 weeks during the first 12 months and every 12 weeks thereafter until the start of new anti-cancer therapy, disease progression, death, lost to follow-up, or withdrawn consent to efficacy follow-up;
12. All patients will be followed for survival status every 12 weeks regardless of treatment discontinuation until death, lost to follow-up, or withdrawal of consent to survival follow-up. Survival follow-up assessment may be made by a phone call to the patient or designated PHI, EPIC medical record review, or certified mail. At least 3 documented attempts should be made to contact the patient before the patient is considered lost to follow-up.
13. The follow-up visit after chemoembolization can be used as day 1 visit of each cycle if the decision is made to continue with LEE011 treatments.

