6.6 DOSE LIMITING TOXICITIES-PHASE IB COMPONENT

The phase Ib component of the study will consist of 3+3 dose escalation rule with the dose of LEE011 escalating up to 600mg daily to determine the maximum tolerated dose (MTD) that will be used during the phase II component. The dose levels for the phase Ib aspect will be 200 mg, 400 mg, or 600 mg daily.

Only the first cycle of therapy (one cycle equals to one month) will be used to determine dose limiting toxicity (DLT). However, if two total grade 5 adverse events or 2 Grade 4 adverse events (lasting ≥ 7 days); occur at any time while the patient is still receiving study treatment that are either: definitely, probably, or possibly related to either LEE011 or TACE the study will be terminated to enrollment.

Only patients started on the first dose of LEE011 will be included in the evaluation of DLT. If a patient has a DLT that patient will not receive further LEE011. Patients following initial chemoembolization who never receive LEE011 will not be included in the MTD analysis and will be replaced. The patients will be followed for thirty days following the initial chemoembolization for safety assessment. Patients will be enrolled into the next highest drug cohort only after 3 or 6 patients have completed the first cycle of therapy. Once the MTD is determined, patients at the MTD dose will continue with LEE011 and represent the first three patients accrued to the phase II aspect.

Due to observed (TACE related, non DLT) toxicity on cohort 1 specific criteria for cohort 1 has been developed after discussion with the FDA. Cohort 1 has been expanded to 6 patients. Decision for dose escalation will be made using the following criteria:

- No or one DLT: the next three patients will be assigned to next higher dose level (400 mg of LEE011).
- At least two toxicities: the MTD is exceeded and the phase I component of the trial will be stopped with no continuation into the phase II component.

For Cohort 2 and 3 the following traditional 3+3 dose escalation rules will be used:

- If a dose limiting toxicity (DLT) is observed in 1 out of 3 patients at a given dose level, up to 3 additional patients will be enrolled and treated at that dose level.
- If 2 out of 3-6 patients at that dose level have DLTs, the dose will be decreased to the previous dose level, and up to 3 additional patients will be enrolled at that dose level for a total of 6 patients.

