- When up to 3 additional patients are added to a given dose level, if 0-1 of 6 patients has a DLT then the dose will be increased to the next dose level.
- Additional dose levels may be explored per investigator discretion to define the safety profile of the treatment.

The recommended Phase II dose (RP2D) will be the highest cohort level in which one or fewer subjects of 6 develops a first cycle DLT.

The Data and Safety Monitoring Committee as described below will regularly review all serious adverse events and any local adverse events, which are unanticipated problems. The study will utilize the Common Terminology Criteria for Adverse Events (CTCAE) version 4.03 for grading of all adverse events related to treatment.

Table 6.2: Dose-limiting toxicity: phase Ib component

The following will be considered a DLT if they occur within the first cycle of therapy with LEE011 and are determined to be possibly, probably or definitely related to LEE011

Grade 4 neutropenia lasting more than 7 consecutive days
Grade 3 or 4 febrile neutropenia
≥ Grade 3 vomiting ≥ 48 hours despite optimal anti-emetic therapy
≥ Grade 3 diarrhea ≥ 48 hours despite optimal anti-diarrhea therapy
Clinical signs of cardiac disease, such as unstable angina or myocardial infarction, or Troponin ≥ grade 3
Grade 4 serum alkaline phosphatase > 7 days
≥ Grade 3 serum creatinine
≥ Grade 3 adverse event for any non-hematologic toxicity unless otherwise specified as below (excluding alopecia, fatigue < 5 days, laboratory abnormalities that are responsive to oral supplementation or deemed by the investigator to be clinically insignificant).

THROMBOCYTOPENIA	
Toxicity/Grade	Dose Limiting Toxicity and Management Recommendations
Grade 3 ($\geq 25 \times 10^9/L$ - $<50 \times 10^9/L$) without clinically significant bleeding	Dose interruption until recovery to grade ≤ 2 . Re-initiate LEE011 at the same dose level. • If toxicity recurs at grade 3: dose limiting toxicity
Grade 3 ($\geq 25 \times 10^9/L$ - $<50 \times 10^9/L$) with clinically significant bleeding	Dose limiting toxicity
Grade 4 ($<25 \times 10^9/L$)	Dose limiting toxicity

HEPATOTOXICITY (BILIRUBIN, ALT, AST)	
TOTAL BILIRUBIN without ALT/AST increase above baseline value	
Toxicity/Grade	Dose Limiting Toxicity and Management Recommendations
Same grade as baseline or increase from baseline grade 0 to grade 1	Maintain dose level with LFTs monitored every other-week

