Increase from baseline grade 0 or 1 to grade 2 ($1.5-3.0 \times$ ULN) or from baseline grade 2 to grade 3 ($>3.0 -10 \times$ ULN)	Dose interruption of LEE011 If resolved to \leq grade 1 in ≤ 21 days, then maintain dose level If resolved to \leq grade 1 in > 21 days or toxicity recurs, then dose limiting toxicity
Increase from baseline grade 0 or 1 to grade 3 ($>3.0-10$ xULN)	Dose limiting toxicity
Grade 4 ($> 10.0 \times$ ULN)	Dose limiting toxicity

Confounding factors and/or alternative causes for increase of total bilirubin should be excluded before dose interruption/reduction. They include but are not limited to: evidence of obstruction, such as elevated ALP and GGT typical of gall bladder or bile duct disease, hyperbilirubinemia due to the indirect component only (i.e. direct bilirubin component $\leq 1 \times$ ULN) due to hemolysis or Gilbert Syndrome, pharmacologic treatment, viral hepatitis, alcoholic or autoimmune hepatitis, other hepatotoxic drugs.

For patients with Gilbert Syndrome, these dose modifications apply to changes in direct bilirubin only. Bilirubin will be fractionated if elevated.

HEPATOTOXICITY (BILIRUBIN, ALT, AST)

AST or ALT without bilirubin elevation $> 2 \times$ ULN

AST or ALT Toxicity/Grade	Dose Limiting Toxicity and Management Recommendations
Same grade as baseline or increase from baseline grade 0 to grade 1 (confirmed 48 to 72 hrs later)	No dose adjustment required with LFTs monitored per protocol if same grade as baseline or bi-weekly in case of increase from baseline grade 0 to 1
Increase from baseline grade 0 or 1 to grade 2 ($> 3.0 - 5.0 \times$ ULN) or from baseline grade 2 to grade 3 ($> 5.0 - 20.0 \times$ ULN)	Dose interruption of LEE011 If resolved to \leq baseline value in ≤ 21 days, then maintain dose level If resolved to \leq baseline value in > 21 days or toxicity recurs, then dose limiting toxicity
Increase from baseline grade 0 or 1 to grade 3 ($> 5.0 - 20.0 \times$ ULN)	Dose limiting toxicity
Grade 4 ($> 20.0 \times$ ULN)	Dose limiting toxicity

AST or ALT and concurrent Bilirubin	
AST or ALT \geq grade 2 ($> 3 \times$ ULN) in patients with normal values at baseline and total bilirubin $> 2 \times$ ULN or AST or ALT \geq grade 3 ($> 5 \times$ ULN) in patients with grade	Dose limiting toxicity

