6.7 LEE011 DOSE MODIFICATION GUIDELINE- PHASE IB CYCLE 2+ AND PHASE II COMPONENTS

Management of severe or intolerable adverse reactions requires temporary dose reduction and/or interruption of LEE011 therapy. Refer to Table 6.3 for guidance. Dose increases once LEE011 has been reduced are not allowed.

Table 6.3 Dose Modification Guidelines

Dose Level	LEE011	
	Dose	Number of capsules & strength
Highest dose (0)	600 mg	3 x 200 mg capsules
First dose reduction (-1)	400 mg	2 x 200 mg capsules
Second dose reduction (-2)	200 mg	1 x 200 mg capsules
Third dose reduction (-3)	Discontinue Treatment of LEE011	

Recommendations for dose reduction, interruption, of discontinuation of LEE011 in the management of adverse reactions are summarized in Table 6-4, Table 6-5, Table 6-6, and Table 6-7. Clinical judgment and discretion of the treating physician should guide the management plan of each patient based on individual benefit and risk assessment.

**Table 6-4 LEE011 Dose Adjustment and Management Recommendations for
HEMATOLOGICAL ADVERSE REACTIONS**

THROMBOCYTOPENIA	
Toxicity/Grade	Dose Adjustment and Management Recommendations
Grade 1 ($\geq 75 \times 10^9/L$)	No dose adjustment required.
Grade 2 ($\geq 50 \times 10^9/L - <75 \times 10^9/L$)	No dose adjustment required.
Grade 3 ($\geq 25 \times 10^9/L - <50 \times 10^9/L$)	Dose interruption until recovery to grade ≤ 2 . Re-initiate LEE011 at the same dose level. If toxicity recurs at grade 3: discontinue LEE011
Grade 4 ($<25 \times 10^9/L$)	Discontinue LEE011.

Toxicity/Grade	Dose Adjustment and Management Recommendations
Absolute neutrophil count (ANC)	
Grade 1 ($\geq 1.5 \times 10^9/L$)	No dose adjustment required.
Grade 2 ($\geq 1.0 - < 1.5 \times 10^9/L$)	No dose adjustment required.
Grade 3 ($\geq 0.5 - < 1.0 \times 10^9/L$)	Dose interruption until recovery to $\geq 1.0 \times 10^9/L$. Re-initiate LEE011 at the same dose level. 
 If toxicity recurs at grade 3: temporary dose interruption until recovery to $\geq 1.0 \times 10^9/L$ and reduce LEE011 dose to the next lower dose level.
Grade 4 ($< 0.5 \times 10^9/L$)	Dose interruption until recovery to $\geq 1.0 \times 10^9/L$. Re-initiate LEE011 at the next lower dose level. 
 If toxicity recurs at grade 4: temporary dose interruption until recovery to $\geq 1.0 \times 10^9/L$ and reduce LEE011 at the next lower dose level.
Febrile Neutropenia	

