6.12.4 CHEMOEMBOLIZATION PROCEDURAL PREPARATION

- a) The patient is prepped and draped in a sterile fashion.
- b) Carefully evaluate the vascular network associated with the lesion with high resolution imaging prior to beginning the embolization procedure.

- c) DC beads are available in a range of sizes, but only 100 to 500 um particles should be utilized. Care should also be taken to choose the appropriate size of DC bead that bases matches the vascular target or vessel size.
- d) Choose a delivery catheter based on the size of the target vessel. DC bead can tolerate temporary compression of 20% to 30% in order to facilitate passage through the delivery catheter.
- e) Introduce the delivery catheter into the target vessel according to standard techniques. Position the catheter tip as close as possible to the treatment site to avoid inadvertent occlusion of normal vessels.
- f) DC are not radio-opaque. It is recommended to monitor the embolization under fluoroscopic visualization by adding the desired amount of contrast medium to the suspension fluid.
 - a. Take care to ensure proper suspension of the DC bead in the contrast medium to enhance distribution during injection.
 - b. Draw the DC bead into a syringe needle of a size greater than or equal to 19 gauge.
 - c. At a rate no faster than 1ml/minute, slowly inject DC bead into the delivery catheter under fluoroscopic visualization while observing the contrast flow rate. Exercise conservative judgment in determining the embolization endpoint.
- g) Upon completion of the treatment, remove the catheter while maintaining gentle suction so as not to dislodge the DC bead still within the catheter lumen.
- h) Discard any unused DC bead loaded with doxorubicin.

6.12.5 **POST-CHEMOEMBOLIZATION PROCEDURE ORDERS AND CARE**

- a) Admit patients overnight for observation.
- b) Hydration with IV normal saline
- c) Patient controlled analgesia for pain control.

6.12.6 **POST-PROCEDURE CARE**

- a) Post-arteriography bedrest with monitoring of vital signs and pulses.
- b) Patient can be discharged as soon as they demonstrate adequate oral intake or liquids, no longer require parenteral narcotics or antiemetics.
- c) Fevers <103 degrees F are normal during the first week following treatment and do not require cultures.
- d) Following institutional guidelines, patients will be seen in the HCC multidisciplinary clinic 7-10 days following chemoembolization and will have the following evaluations completed:

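### Phase Ib cycle 1 has one mid-cycle blood draw in Table 7.1, too sparse to be sure of detecting the two DLTs that require more than 7 days at grade 4

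*Combined protocol and SAP*

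**What the plan says.** Section 6.6 limits the DLT window: "Only the first cycle of therapy (one cycle equals to one month) will be used to determine dose limiting toxicity (DLT"). Within that window, Table 6.2 lists two laboratory DLTs defined by duration: "Grade 4 neutropenia lasting more than 7 consecutive days" and "Grade 4 serum alkaline phosphatase > 7 days". It also interrupts LEE011 in cycle 1 for certain platelet, bilirubin and AST/ALT rises. For bilirubin and AST/ALT, slow resolution (more than 21 days) or recurrence becomes a DLT: "days or toxicity recurs, then dose limiting toxicity".

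Table 7.1 places CBC and CMP on cycle 1 day 1, cycle 1 day 15 and cycle 2 day 1. Footnote 4 allows 3 days either side. Footnote 2 contains two further provisions:

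- Weekly laboratory work after a dose change or halt, worded for phase II: "If there are any dose modifications or halting of drug in the phase II aspect, weekly hematology, comprehensive metabolic panels".
- CBC and CMP after chemoembolization, with no phase restriction: "following each chemoembolization the following will be done every other week for two cycles after each chemoembolization". No starting day is given for the count.

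The neutropenia management table (Table 6-4) falls under a section headed "LEE011 DOSE MODIFICATION GUIDELINE- PHASE IB CYCLE 2+ AND PHASE II COMPONENTS", so it does not govern phase Ib cycle 1. Section 9.3 requires adverse events and abnormal laboratory values to be monitored until they resolve. Section 7.4.2 requires the same, to resolution or stabilization, after an interruption or discontinuation. Neither gives a sampling interval.

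**The concern.** A duration criterion can be applied only if values are drawn often enough to show that the abnormality occurred and persisted. Here the scheduled spacing is twice the duration threshold. The clause that would tighten sampling after a drug halt is written for phase II, where no DLT decision is made, and is missing from the phase in which DLTs decide the dose.

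The cycle 1 DLT count decides escalation at each level and, through the rule of one or fewer DLTs in 6 patients, the recommended phase II dose. A grade 4 episode that falls between draws is not counted, and no sampling gap can add a DLT. The error therefore runs one way, towards escalation. Marrow suppression is the expected toxicity: section 1.7.4 reports grade 3/4 neutropenia in 15 of 67 patients (22%) on LEE011 600 mg, and section 1.6 reports 43% in HCC patients on another CDK4/6 inhibitor.

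**Working it through.** The plan states no detection figure, so there is none to reproduce. The check asks how often the scheduled draws fall inside a qualifying episode.

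**Inputs from the documents.** Post-baseline draws on day 15 and nominal day 29 (Table 7.1). Window of 3 days either side (footnote 4). Threshold of more than 7 days (Table 6.2). LEE011 starts between 7 and 28 days after chemoembolization (section 6.12).

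**Assumptions.** Draws occur on nominal days, with no unscheduled draws. Onset day *s* is uniform over days 2-21 (20 possible days) or, as a sensitivity case, days 8-21 (14 days). The later range allows for steady state at about day 8 (section 1.7.4.1).

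**Step 1: spacing.** 29 − 15 = 14 days. With the window, day 12 to day 32 gives up to 20 days.

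**Step 2: sampling on Table 7.1 alone.** An episode of *d* days occupies days *s* to *s* + *d* − 1. It is sampled if that run contains day 15 or day 29.

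- *d* = 8: onset on days 8-15. That is 8/20 = 40%, or 8/14 = 57%.
- *d* = 10: onset on days 6-15 or 20-21. That is 12/20 = 60%, or (8 + 2)/14 = 71%.
- *d* = 12: onset on days 4-15 or 18-21. That is 16/20 = 80%, or (8 + 4)/14 = 86%.

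**Step 3: weekly draws (days 8, 15, 22, 29).** Any run of 8 days contains one draw day, so sampling is 100% for all three durations under both onset ranges.

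**Step 4: footnote 2's post-chemoembolization draws.** If they are counted from the procedure at 14-day intervals, and LEE011 day 1 is *L* days after it, they fall on LEE011 days 15 − *L*, 29 − *L*, 43 − *L* and so on.

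| Lag *L* (days) | Added draw days | 8-day episodes sampled (onset days 2-21) |
|---|---|---|
| 7 | 8, 22 | 100% |
| 8 | 7, 21 | 100% |
| 9 | 6, 20 | 90% |
| 10 | 5, 19 | 80% |
| 14 or 28 | none (coincide with days 1, 15, 29) | 40% |

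**Step 5: what required follow-up can recover.** Suppose follow-up under sections 9.3 and 7.4.2 were daily from the first scheduled grade 4 value, on day *x*. The observed span exceeds 7 days only if *s* + *d* − *x* > 7.

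- Table 7.1 draws: 1/20, 3/20 and 5/20 onsets qualify for *d* = 8, 10 and 12 (5%, 15%, 25%). For onset on days 8-21: 1/14, 3/14 and 5/14 (7%, 21%, 36%).
- Weekly draws: 2/20, 8/20 and 14/20 (10%, 40%, 70%). For onset on days 8-21: 2/14, 6/14 and 10/14 (14%, 43%, 71%). Repeats every 2 or 3 days give the same counts, because the visit 7 days after the first grade 4 value settles the matter.

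Weekly sampling thus closes the detection gap and narrows the dating gap, but does not remove the latter.

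**The case against.** The strongest reply is that the protocol already requires follow-up. Sections 9.3 and 7.4.2 apply in both phases, so an episode seen on day 15 will be pursued. A reader might note that no episode shorter than 14 days contains two Table 7.1 draws on nominal days, and infer that no such episode can be classified as a DLT. The documents do not support that inference: unscheduled follow-up values are required and would count. What stands is that no interval is set, follow-up begins only after a value has been drawn, and it cannot recover the onset date.

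The second reply is that footnote 2's post-chemoembolization draws may already do much of the work. Section 6.12.6 says "patients will be seen in the HCC multidisciplinary clinic 7-10 days following chemoembolization", with the decision to start LEE011 made then. At lags of 7 to 10 days, counted from the procedure, 8-day episodes are sampled in 80-100% of onsets. This stands, and it narrows the point considerably. It depends on an anchor the text does not state. Footnote 13 also lets the post-procedure visit serve as day 1, and the added draws vanish at lags of 14 or 28 days.

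A reader might also infer that the dose chosen for phase II will be too high, or seek the added probability of escalating. The documents do not supply the rate of grade 4 neutropenia lasting more than 7 days in cycle 1, only a combined grade 3/4 figure, so no such number can be fixed.

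**Conclusion.** The point holds as a gap in ascertainment, not as a demonstrated error in the dose. Table 7.1 alone leaves 60%, 40% and 20% of 8-, 10- and 12-day episodes unsampled with onset uniform over days 2-21, and 43%, 29% and 14% with onset over days 8-21. These figures assume nominal visit days and no unscheduled draws. The 14-day spacing and the restriction of weekly repeats to phase II do not depend on those assumptions.

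The direction of bias is certain and its size is not. It is bounded: the planned levels stop at 600 mg, the recommended single-agent dose; febrile neutropenia is a DLT without a duration test; and section 16.0 provides for real-time toxicity review, although that review sees only values that were drawn. The change is worth making because it is cheap and because these DLTs decide escalation.

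**What to change.** - In phase Ib cycle 1, draw CBC with differential and CMP on days 1, 8, 15, 22 and 29, and require the day 29 result before the escalation decision.
- Remove the phase II restriction from the weekly-repeat clause in footnote 2, so that it also covers the cycle 1 halts in Table 6.2.
- After any grade 4 neutrophil or alkaline phosphatase value, repeat every 2-3 days until grade 3 or lower.
- State that the every-other-week post-chemoembolization draws may be met by these visits.
- Keep the DLT definitions as written. Onset should not be imputed to a date before the first grade 4 value, because that would count some episodes of 7 days or less and so change the endpoint.

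Cost: up to two extra routine draws per phase Ib patient (days 8 and 22). For 9 to 18 patients that is 2 × 9 = 18 to 2 × 18 = 36 draws in total, plus repeats only after a grade 4 value or a halt. The phase II sample size is unaffected.
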